### *Measures for Specific Aim 1.*

#### **Motor performance**

1. *Fitness Level:* We will assess physical fitness level using a cycle ergometry assessment of maximal volume of oxygen consumption. This is described in detail below.
2. *Purdue Peg Board Task:* The Purdue Pegboard measures unimanual motor dexterity. The test consists of two parts: 1) placing pins in a column of holes and 2) an assembly task using three components (pin, washer, collar). The participant is asked to place as many items as possible in 30 or 60 seconds, respectively.
3. *Nine Hole Peg Board Task:* A standard dexterity assessment, this task asks participants to place and remove pegs on a nine-hole pegboard as quickly as possible.
4. *Pinch and Grip Strength:* FDI and hand strength will be assessed using standard dynamometer (JAMAR) squeeze tests.
5. *Coin rotation task:* Another dexterity assessment, this task asks participants to rotate a coin (U.S. nickel) as quickly as possible for 20 rotations.
6. *Halstead finger tapping:* The Halstead finger tapping test is a standard test for testing psychomotor speed. The participant is asked to press a lever attached to a counter as many times as possible in 10 second trials.
7. *Jebsen Taylor hand function test:* The Jebsen Taylor hand function test is a timed 7-part assessment of common motor abilities performed with the dominant hand.
8. *Hand steadiness test:* A standard occupation therapy test measuring hand steadiness over a brief time interval (10 seconds).
9. *Poffenberger Crossed-Uncrossed Difference Test:* The Poffenberger paradigm is a test of transcallosal transfer time during reaction time responses. This 200-trial test compares reaction time based on hand of response and spatial presentation of stimulus cue.
10. *Target force matching:* The target force matching task is similar to the anisometric FDI muscle training used in the behavioral intervention. A computer presents a target force marker and the participant's task is to match the cued lift load target and hold for a set period of time. EMG is of the FDI taken during this assessment.
11. *Motor tracking:* The motor tracking task is a computer based presentation of a stimulus (vertical bar) moving laterally. The participant is instructed to track the

movement of the stimulus using a computer cursor controlled by a touchpad input device.

**Specific Aim 2) To assess the effects of the aerobic activity on interhemispheric inhibition using fMRI and TMS.**

*Introduction.* The PI's previous research line has indicated that increased aerobic activity level is associated with decreases in aging-related loss of interhemispheric inhibition ([name] et al., 2009; [name] et al., 2011). In a previous project, we have noted that in fMRI, highly-fit elderly and middle age adults show lower bilateral positive BOLD activity in the primary motor cortex. Further, highly fit individuals show patterns of activity more similar to younger adults in that they show a negative BOLD signal in the ipsilateral primary motor area likely indicating an active suppression. In TMS, highly fit elderly and middle age adults show a longer duration of the ipsilateral silent period, a putative measure of transcallosal inhibition (Meyer et al., 1995).

We will test the hypothesis that an aerobic activity intervention can mitigate or reverse aging-related loss of interhemispheric inhibition as measured by fMRI and TMS. We will also test the hypothesis that behavioral training of unimanual activity acts to alter interhemispheric communication dynamics and this is a potential mechanism of improvement in motor performance.

*Research Design and measures.* fMRI and TMS paradigms are discussed below.

*fMRI tasks.* Two block-design right-hand motor tasks will be used to evaluate interhemispheric cortical activation patterns. Both tasks have been reported sensitive to aging-related differences in interhemispheric inhibition ([name] et al., 2009; Ward et al., 2008). Blocks will consist of seven images (28 seconds) for both rest and active conditions and six block cycles (alternating between 7 rest images and 7 active images) will comprise each run (5 minutes 36 seconds). In the scanner, participants will engage in two runs of each motor task and all performance data (accuracy, reaction times) will be saved for later analysis. Participants will train on the both tasks outside of the scanner and again inside the scanner immediately prior to data acquisition. Mirror movements (symmetric movement of the opposite hand) are of concern for unimanual digit manipulations. To monitor for such movements, force output of the left first dorsal interosseous muscle (FDI) will be recorded during practice sessions.

*Finger opposition motor task:* The first motor task will be a block presentation of a repeated button press using opposition of the index finger and thumb. This task has been shown to exhibit a negative BOLD response in ipsilateral primary motor cortex (M1) in younger adults at spatial resolutions comparable to those planned for the present investigation. Performance of similar tasks in sedentary elderly samples, however, shows positive BOLD responses in ipsilateral M1 ([name] et al., 2011). Participants will fixate gaze on a central point of a computer screen throughout each of 2 runs. Blocks will be cued by the change of fixation shape varying between a red octagon (rest condition) and a green circle (movement condition). During the movement condition, participants will be instructed to time button presses with a flashing visual

stimulus (2 Hz). Participants are instructed to press a button until a tactile click is obtained (at 3N of force) before repeating the task.

*Force matching task.* A second motor task will be employed to potentially differentiate the effect of muscle recruitment on patterns interhemispheric activity. As previous studies (e.g. - Ward et al., 2008) have indicated that increasing muscle recruitment may influence levels of ipsilateral inhibition, the inclusion of a target force matching task of varying intensities may quantitatively inform such activity. In this task, we will ask participants to match grip force to a target level set at a percentage of the participants' maximum voluntary contraction (MVC). During scanning, participants will perform a series of dynamic isometric pinch squeezes with the dominant right hand using a MRI-compatible manipulandum built by the applicant. Continuous visual feedback about the force exerted (represented as a vertical bar) will be provided throughout the scanning session. Prior to scanning, but while lying in the scanner, participants will use a pinch squeeze of the manipulandum to generate their MVC for each hand. Within trial blocks, target force for the hand grip will be visually cued using horizontally presented line parallels with vertical offset equal to  $\pm 3\%$  (relative to MVC). Target forces for active response blocks for each of two runs will be 25% and 35% of MVC, respectively.

*TMS.* Both single and paired pulse TMS measures will be taken for the current study to assess cortical excitability and interhemispheric communication. Paired-pulse TMS requires the use of multiple stimulators, to which [name] has granted unfettered access for the duration of the study. All TMS procedures will be completed in [name] VA laboratory.

*Single pulse measure.* Four single-pulse TMS measures will be taken: size and latency of Motor Evoked Potential (MEP) in right FDI muscle at resting motor threshold, duration of ipsilateral silent period (iSP), and MEP recruitment curves (RC). Electromyography (EMG) will be taken from the FDI muscle on both hands. Muscle activation will be monitored with a real-time oscilloscope software package (Scope; ADInstruments Ltd). A Magstim 200 magnetic stimulator (The Magstim Company Ltd, Carmarthen, UK) and a focal figure of 8 coil will be used to stimulate the left primary motor cortex during the initial mapping procedure. The coil will be placed tangential to the scalp with the handle pointing backwards and  $45^\circ$  away from the midline for stimulation. The scalp site corresponding to the lowest stimulator output sufficient to generate a magnetic evoked potential of at least 50 mV in 6 out of ten trials will be defined as the area of lowest motor threshold (LMT), also known as the "hotspot". The MEP size measure will be taken using ten stimulations of the left primary motor area FDI hotspot at LMT. The right FDI motor hotspot will be assessed using the same procedure, but with the left hand and stimulation delivered to the right motor cortex.

The ipsilateral silent period will be determined using a longstanding method (Wasserman et al. 1991). For ipsilateral silent period, the left FDI muscle will be contracted via pinch grip at 25% maximal voluntary contraction (determined by grip dynamometer) and an 80% LMT stimulus will be delivered to the left primary motor area

FDI "hotspot", previously determined by an initial sensitivity assessment. Stimulator output equivalent to 150% LMT is delivered to the left FDI hotspot.

FDI recruitment curves, a measure of cortical excitability, will be generated by stimulation at the LMT hotspot over progressively increasing intensities. Testing proceeds by placing the coil at the hotspot and recording 5 stimuli in 10% increments beginning at an intensity of 10% below LMT threshold. Data collection for the RC will be terminated when a plateau of the sigmoidal curve is observed. The slope of the RC will be generated from the data using linear regression.

*Paired-Pulse measures.* The paired pulse procedure) interhemispheric inhibition assessment (Ferber et al., 1992 requires a second Magstim 200 magnetic stimulator and attached figure of 8 coil. In this procedure, hotspots on both motor cortices are target for stimulation in a paradigm assessing the effects of stimulation of one laterality on the opposite cortex's output MEP after its stimulation. For this procedure, a "conditioning" TMS pulse is applied to the right motor cortex at either 10 or 40 milliseconds prior to a "test" pulse's administration to the left motor cortex. As a result of the conditioning stimulation, the test MEP's response amplitude (in the right FDI muscle) is lowered due to interhemispheric inhibitory processes. Both 10 and 40 ms durations will be tested in this protocol. Magnitude and duration of IHI increase with the intensity of the conditioning stimulus (Ferber et al., 1992). As such, the intensity of the conditioning stimulus will be varied from 100 to 150% of resting motor threshold in 10% steps (i.e., six different intensities) to obtain a range of IHI magnitudes from threshold to maximum. Test pulse intensity will be adjusted to produce an unconditioned MEP of on average 1 mV in peak-to-peak amplitude. Testing will be comprised of eight trials per intensity and eight unconditioned test stimulus trials (i.e., total of 56 trials), applied in pseudo-randomized order. The intertrial interval will vary randomly between 4 and 6 s to reduce anticipation of the next trial. Conditional averages of the single-trial MEP peak-to-peak amplitudes will be calculated.

*Functional Imaging and Neurophysiological Analyses.* Functional images will be analyzed and overlaid onto structural images with the Analysis of Functional Neuroimaging (AFNI) program (Cox, 1996). To minimize the effects of head motion, time series images will be spatially registered in 3-dimensional space. The average functional intensity of each acquired slice for every subject will be normalized to the mean intensity of all slices for all subjects to control for differences in functional intensity between subjects. A subject's data will be excluded from further analyses if any time series of a subject is judged from visual inspection to contain a significant number of images with gross artifacts or residual motion.

*fMRI Analysis.* The current study is concerned with the response of the ipsilateral primary motor cortex during actions performed by right hand. It is hypothesized that sedentary aged adults will initially show an increase in metabolic activity (i.e. – a positive BOLD response) in this area. To assess this, an analysis of average hemodynamic (impulse) response functions in the right primary motor cortex will be performed. These impulse response profiles will be tested across session using repeated measures ANOVA. Significant differences will be assessed at the individual

subject and group level.

For group analysis of intervention effects, anatomic and functional images will be interpolated to volumes with 1 mm^3 voxels, co-registered, and converted to stereotaxic space of Talairach and Tournoux (1988) using AFNI. Estimates of hemodynamic response functions (HRFs) generated from a deconvolution procedure will be spatially smoothed using a 5 mm full-width half-maximum (FWHM) Gaussian filter to compensate for variability in structural and functional anatomy across participants. Area under the curve (AUC) of the HRF's will be entered into a voxel-wise two-way mixed-design ANOVA (age grouping as the between subjects factor, session as the within-subjects factor). Additional pair-wise comparisons of age groupings will be performed using Student's t-test ( $p < .05$ , False Discovery Rate corrected) on a voxel-by-voxel basis with left and right primary motor cortices selected as regions of interest (ROI). Pairwise comparisons will be computed for all motor response conditions.

*TMS Analysis.* Six measures will be computed and analyzed from TMS acquisitions: Right FDI MEP size, right FDI MEP latency, recruitment curves (RC), ipsilateral silent period (iSP), interhemispheric inhibition at 10ms (IHI10) and 40ms (IHI40). The size of left FDI MEP evoked by TMS will be measured from peak-to-peak between TMS stimulation (first peak) and subsequent muscle response (second peak). The latency of MEPs will be measured from the onset of the stimulus presentation to the onset of the MEP. Recruitment curves will be evaluated based on slope generated from linear regression. Onset and end latency of the iSP will be taken at the initial and final intersections of the averaged signal with baseline indicating 80% of the background EMG level; the duration of EMG suppression between these two points will be computed. For each of the stimulation intensities, IHI will be expressed by  $(1 - \text{mean conditioned MEP} / \text{mean unconditioned MEP}) \times 100\%$ . Accordingly, IHI = 0%, IHI = 100%, and IHI < 0% will indicate no inhibition, complete inhibition, and interhemispheric facilitation, respectively. For within subjects comparison, repeated measures ANOVA with subsequent repeated measures pairwise t-tests will be generated. Group comparisons of TMS measures will be analyzed by between-subjects ANOVA and subsequent t-test pairwise comparisons. For all test, p-values < 0.05, corrected for multiple comparisons where applicable, will be considered statistically significant.

*BDNF Evaluation.* Fasting whole blood will be collected, by a certified phlebotomist, via venipuncture or peripheral venous line into pre-cooled plasma EDTA tubes and serum separator tubes (~40 ml per visit). Following collection, tubes will be transferred in sealed biohazard bags and in according with blood borne pathogens training standards to the Molecular Biology Lab (4A 178/4A 167) of the Atlanta VAMC Center of Excellence.

Plasma volume will be measured using methods described by Dill and Costill. Lactate will be measured by the Accusport Lactate Analyzer (Roche Molecular Biochemicals, Mannheim, Germany). Serum samples will be allowed to clot for 30 minutes before centrifugation at 1000g for 15 minutes. Plasma samples will undergo centrifugation within 30 minutes of collection at 1000g for 15 minutes at 2-8°C. Plasma aliquots will be separated and will then undergo an additional centrifugation "Super-

Spin” at 10,000g for 10 minutes at 2-8°C in order to completely remove platelets. Serum and plasma samples will be stored at –80°C. Serum and plasma aliquots will be analyzed for measures of interest as determined by ELISA (R&D Systems, Minneapolis, MN). All assays will be performed in duplicate and in a single run.

The procedure below describes the blood collection timeline during the 12-week intervention period and follow up:

*Baseline:* 4 measurements over 1 hour, taken every 15 minutes, to demonstrate reliability of the measures. (Assessment 1, Day 1)

*Week 1:* Taken immediately prior to exercise, immediately post, 15 min post, 30 min post. (Intervention 1)

*Week 4:* Taken immediately prior to exercise, immediately post, 15 min post, 30 min post. (Intervention 1)

*Week 8:* Taken immediately prior to exercise, immediately post, 15 min post, 30 min post. (Intervention 1)

*Week 12:* Taken immediately prior to exercise, immediately post, 15 min post, 30 min post. (Intervention 1)

*Follow-up:* 1 measurement taken at 12-week follow-up. (Assessment 5, Day 1)

[figure not shown]
All blood draws will be conducted in the Movement Studies Laboratory (Intervention site) at the Atlanta VA Medical Center. Tubes will be coded and thus have no identifiable patients information. The master code list will be maintain in a locked file cabinet in the office of the PI (12C115).

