## 7. Statistical Analysis

**Statistical Analysis for Specific Aim 1.** We will model each of the outcome measures in Aim 1 (upper extremity) jointly using a mixed linear model to determine whether the mean responses of the groups are significantly different across the time points. We expect that modeling the outcomes jointly, using subject as a random factor, will allow for some gains in power. Our fixed factors will be time, treatment group and their interaction. This model will enable us to estimate the overall effects of time and treatment, and most importantly, how the effects of treatment differ with time.

**Statistical Analysis for Specific Aim 2.** For each of the outcome measures in Aim 2 (changes in fMRI and TMS activity during unimanual tasks) we will use a mixed linear model to determine whether the mean responses of the groups are significantly different across the time points. Our fixed factors will be time, treatment group and their interaction. This model will enable us to estimate the overall effects of time and treatment, and most importantly, how the effects of treatment differ with time.

**Statistical Analysis for Specific Aim 3.** For each of the outcome measures in Aim 3 we will use a mixed linear model to determine whether the mean responses of the groups are significantly different across the time points. Our fixed factors will be time, treatment group and their interaction. This model will enable us to estimate the overall effects of time and treatment, and most importantly, how the effects of treatment differ with time. Level of interhemispheric inhibition will be characterized by proportion of ipsilateral motor cortex recruited during fMRI tasks, ipsilateral silent period in TMS, and level of diminution of MEP size in the interhemispheric inhibition protocol in paired-pulse TMS.

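### The two fMRI force levels are tied to run order with no counterbalancing stated, so the secondary 35% versus 25% contrast cannot be separated from order effects on the task response

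*Combined protocol and SAP*

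**What the plan says.** Section 5, Specific Aim 2 describes two fMRI motor tasks. The paragraph on fMRI tasks states that "participants will engage in two runs of each motor task". It describes each run as six cycles "alternating between 7 rest images and 7 active images) will comprise each run (5 minutes 36 seconds"). Only rest and active blocks alternate within a run.

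The force-matching paragraph gives the reason for the second task: "A second motor task will be employed to potentially differentiate the effect of muscle recruitment on patterns interhemispheric activity". It adds that "the inclusion of a target force matching task of varying intensities may quantitatively inform such activity". The force levels are then set: "Target forces for active response blocks for each of two runs will be 25% and 35% of MVC, respectively".

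Neither paragraph says that the order of the two runs is varied within a scan, between sessions or between participants. By contrast, the paired-pulse TMS paragraph in the same section does specify a pseudo-randomised trial order.

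On analysis, the fMRI Analysis paragraph says that "Pairwise comparisons will be computed for all motor response conditions". For Aim 2, Section 7 says: "Our fixed factors will be time, treatment group and their interaction". Neither place names force level or run order as a factor.

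**The concern.** The second task varies force so that the role of muscle recruitment in ipsilateral activity can be examined. That is a comparison of 35% with 25% of maximum voluntary contraction (MVC). If 25% is always the first run and 35% always the second, anything that changes the task response between runs enters the comparison in full. Fatigue is plausible, because older sedentary participants have just produced maximal contractions in the scanner and then perform repeated pinch squeezes. Habituation is also plausible.

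A difference between force levels could then be read as an effect of recruitment when it is an effect of order, or an order effect could hide a real one. No later analysis can repair this without assuming that the run effect is zero.

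**Working it through.** **Inputs.** Two runs per task, 7 images in 28 s per block, six rest-active cycles per run (fMRI tasks paragraph). One target force per run, 25% and 35% of MVC (force-matching paragraph). 40 participants (Research Design, Aim 1). Five assessments: enrolment, after the waiting period, after each of the two interventions, and after the final six months.

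**Run structure.** 28 s / 7 images = 4 s per image. 6 × (28 + 28) s = 336 s = 5 min 36 s, which matches the stated run length. Two runs give 12 active blocks, six at each force level. The stated structure leaves no change of force within a run.

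**Fixed order.** Let f be the effect of 35% relative to 25%, and r the effect of the second run relative to the first. In every participant the difference between runs is

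D = f + r.

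Only the sum is observed. With 40 participant intercepts, one run-order column and one force column, the design matrix is 80 × 42. It has rank 41, and the run-order and force columns correlate at 1.0.

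**More sessions do not help.** Repeating the same order at five sessions, with group, session, force, their interactions and a run term, gives a 400 × 21 matrix of rank 20. It is still one short.

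**Counterbalanced order.** If half take 25% first and half take 35% first, second run minus first run is

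- 25% first: D₁ = r + f
- 35% first: D₂ = r − f

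so f = (mean D₁ − mean D₂) / 2. With 20 participants in each order the matrix has full rank (42 of 42) and the correlation is 0.

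**Precision.** Let σ² be the residual variance of one run, so that a difference between two runs has variance 2σ².

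- Counterbalanced: Var(f) = (2σ²/20 + 2σ²/20) / 4 = 0.05σ².
- Fixed order: Var(mean D) = 2σ²/40 = 0.05σ², but this estimates f + r.

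Counterbalancing therefore separates f from r without loss of precision.

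**What the fixed order leaves intact.** At a given force level, every participant in both arms does that run in the same position at every session. The run effect is common to both arms and cancels from the between-arm difference in change over sessions.

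**The case against.** The best case on the other side has five parts.

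- **The order is inferred.** The protocol never says first and second run, and an operating procedure might already vary them. This stands as a limit: the rank results assume a fixed order and do not prove one. But the listed order is the natural reading, and the plan states no control.
- **The force question is minor.** The purpose is worded tentatively, Section 7 has no force term, and the sentence on pairwise comparisons follows one about group comparisons, so it may mean groups within each condition. This stands. A reader might infer that the main Aim 2 comparison is compromised. The documents do not support that, because order is the same in both arms.
- **Some order effects are already handled.** Each run has its own rest blocks, which remove simple shifts in baseline signal. Participants practise outside the scanner and again inside it just before acquisition, which reduces practice effects. This stands, so it would be too strong to say that drift and practice fall wholly on the contrast. Fatigue and habituation in the active response remain.
- **Losing one run.** A reader might infer that an unusable run removes a whole force level at that visit, and that mixing levels within runs would rescue it. The image-processing paragraph instead excludes a participant's data if any of their time series shows substantial artefact or motion. The argument therefore has little force here.
- **Change in the force effect.** Change by arm or session in the 35% versus 25% contrast is estimable if the run effect is constant. This is correct, but it is an assumption. The behavioural programme trains the first dorsal interosseous, a hand muscle, under load and could alter second-run fatigue.

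**Conclusion.** The point holds as a cheap design improvement to a secondary, mechanistic contrast. If the runs are done as listed, the 35% versus 25% comparison is completely confounded with run order at each assessment. The size of any resulting bias equals the run effect r, which the documents give no means to estimate.

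The conclusion rests on one reading: the same order, 25% then 35%, in every scan. If the order is already varied in practice, only the protocol text needs correcting.

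It does not extend to the between-arm change over sessions at each force level, which the fixed order does not bias. The counterbalanced estimate also has its own assumption: that the run effect is the same whichever force came first. If 35% in the first run tires participants more than 25% does, part of that carry-over would remain in the contrast.

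**What to change.** In the force-matching paragraph of Section 5, state that the order of the 25% and 35% runs is counterbalanced across participants within each arm. With the planned 20 per group, that means ten in each order. State also that each participant keeps the same order at every session, so that within-participant change is undisturbed. In the fMRI Analysis paragraph or Section 7, state that any analysis of force level includes a run-order term.

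Mixing both levels within each run, with three 25% and three 35% blocks per run, is an acceptable alternative that keeps six blocks per level, but it is not required.

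The cost is a small change to the stimulus script, a few sentences of protocol text and no added scan time. There will be slightly more variation between participants at each force level, because half perform it first and half second. The run-order term absorbs this.

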*Research Design.* The proposed study will examine 40 older, sedentary Veterans from the greater Atlanta area. Participants will be randomly assigned to one of two 15-month intervention conditions involving aerobic fitness training and behavioral training. The study is a reversal design in which both groups are assessed pre-treatment with both fMRI and TMS measures, as well as behavioral measures at study enrollment. As part of the design, both groups will undergo a 3-month waiting period during which they will engage in an organized stretching routine with no aerobic exercise component. After this waiting period, the participants again undergo behavioral, fMRI and TMS assessments. At this point, the participants will be assigned to either a behavioral treatment group involving a motor coordination protocol previously shown to improve upper extremity motor performance in older adults (Christou et al, 2011) or a supervised aerobic training group at the Atlanta VA Medical Center. The design of the study is depicted in the in Figure 6 below. The primary outcomes of this aim are changes in fMRI and TMS measures of interhemispheric communication and motor performance tests.

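### The ipsilateral silent period is given two stimulus intensities (80% and 150% LMT) with no statement of which applies, and the MEP-size rule scores an unlisted muscle from the stimulus

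*Combined protocol and SAP*

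**What the plan says.** **Acquisition.** Section 5, Specific Aim 2, Single pulse measure, has the participant contract the left FDI at 25% of maximal voluntary contraction. It then states that "an 80% LMT stimulus will be delivered to the left primary motor area", at the FDI hotspot. The next sentence, which closes the paragraph, is "Stimulator output equivalent to 150% LMT is delivered to the left FDI hotspot". The text does not call these two conditions, give either a purpose, or state a number of trials for each.

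**Scoring.** TMS Analysis takes silent-period onset and end where the averaged signal crosses "baseline indicating 80% of the background EMG level; the duration of EMG suppression between these two points will be computed". It names no stimulus intensity for this measure. The 80% there is a cut-off on background EMG, not a stimulator setting.

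**MEP size.** Single pulse measure specifies MEP size in the right FDI, evoked by stimulating the left motor area. The list of six measures that opens TMS Analysis also says right FDI. The sentence that defines the measurement says left FDI, and takes the TMS stimulation as the first peak and the muscle response as the second.

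**The concern.** Two settings for one measurement, at one site, with no rule for choosing between them, leave the acquisition undefined. Staff could follow either sentence and be within the protocol.

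The measure carries weight. Under Specific Aim 1, Research Design says: "The primary outcomes of this aim are changes in fMRI and TMS measures of interhemispheric communication and motor performance tests". For Aim 3, Section 7 characterises interhemispheric inhibition by three measures: the fMRI recruitment proportion, and "ipsilateral silent period in TMS, and level of diminution of MEP size in the interhemispheric inhibition protocol in paired-pulse TMS".

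If intensity changed between sessions, it would add noise. If it changed at the same session in both groups, it would shift the within-subject comparisons that TMS Analysis plans. The plan accepts that intensity matters for a related measure: "Magnitude and duration of IHI increase with the intensity of the conditioning stimulus". That sentence concerns the paired-pulse measure and gives no size for the silent period.

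The MEP-size rule is a secondary matter. Followed literally, it scores a muscle that is not on the list and includes the stimulus in the amplitude.

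**Working it through.** The plan gives no figure to reproduce here, so the check is mainly a comparison of text.

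**1. Is it the same site?** Single pulse measure says the "right FDI motor hotspot will be assessed using the same procedure, but with the left hand and stimulation delivered to the right motor cortex". Hotspots are therefore named by hemisphere, and the left FDI hotspot is in the left motor cortex, the site of the 80% sentence. If the label were read by muscle instead, the pulse would go to the right cortex. That is contralateral to the contracting left FDI, so the response would not be ipsilateral.

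**2. Could 150% belong to another measure?** None fits.
- MEP size is taken at LMT.
- Recruitment curves start 10% below LMT and rise in 10% steps to a plateau, with no fixed 150% setting.
- Paired-pulse conditioning goes to the right cortex. The left-cortex test pulse is set to give an unconditioned MEP of about 1 mV.

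**3. Could they be two intended conditions?** Where the plan wants several intensities, it lists them. Paired-Pulse measures gives six conditioning intensities with eight trials each plus eight unconditioned trials: 6 × 8 + 8 = 56, as stated there. TMS Analysis counts the silent period once among its six measures, while the 10 ms and 40 ms inhibition measures are counted separately. The Section 7 models have time, treatment group and their interaction as fixed factors, with no intensity term.

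**4. How far apart are the settings?**
- Difference: 150 − 80 = 70 points of LMT.
- Ratio: 150 / 80 = 1.875.
- The site that defines LMT is the one "corresponding to the lowest stimulator output sufficient to generate a magnetic evoked potential" meeting the response criterion. So 80% lies below that output and 150% above it. The criterion concerns evoked responses, so this alone does not show what silent period either setting would produce.

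**5. How many measurements?**

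| Assessment | Source | Count |
|---|---|---|
| Enrolment; end of waiting period | Aim 1, Research Design | 2 |
| After each 12-week intervention | Research Plan | 2 |
| After the six-month phase | Aim 3, Research Design | 1 |
| Total | | 5 |

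For 40 participants, 5 × 40 = 200 determinations. This reads imaging and neuroimaging as including TMS, as the Research Plan does at its first mention.

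**6. MEP size.** Two statements say right FDI (Single pulse measure and the TMS Analysis list); the measuring rule says left. Paired-Pulse measures uses the MEP's own peak-to-peak amplitude; the rule in TMS Analysis runs from stimulus to response.

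No power loss is computed, because the documents give no effect of intensity on silent-period duration.

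**The case against.** The textual conflict is hard to dispute. The case against is about consequence.

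- **Harm needs drift.** If one intensity is used at every session, nothing is lost. All TMS is done in one laboratory under a method described as long established, which makes unnoticed switching less likely. This stands as a limit on the harm, but it does not tell the operator which setting to use. The documents do not reproduce the cited method, so it cannot settle the matter.
- **The main model is partly protected.** Section 7 puts most weight on the group-by-time interaction. An equal additive shift in both groups at one session goes into the time effect and largely cancels from the interaction. This also stands. It does not protect the time effects, the repeated-measures comparisons in TMS Analysis, or the Aim 3 expectations in Section 4 that refer back to the 9-month and enrolment assessments.
- **Primary status is loosely worded.** Research Design names TMS measures generically, the Aim 1 measure list contains none, and Section 7 describes Aim 1 outcomes as upper extremity. The primary label should not be pressed for the silent period alone. Its role in Aim 3 is explicit.
- **The count measures exposure, not damage.** Agreed. It also depends on the enrolment figure: Section 7 plans 24 per group, which would give 5 × 48 = 240.
- **The MEP wording may be a slip.** Possibly, and it is recoverable, since EMG is recorded from both hands. MEP size is also not one of the three inhibition measures. As written, the rule still contradicts the list above it.

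**Conclusion.** The concern holds. The protocol assigns the ipsilateral silent period both 80% and 150% LMT at the same cortical site and does not present them as conditions. Neither TMS Analysis nor any other section resolves this. The settings differ by 70 points of LMT (ratio 1.875) and lie on opposite sides of the plan's own threshold. The measure is planned at five assessments, 200 determinations if 40 participants complete all of them.

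The consequence is conditional: added noise or shifted within-subject comparisons if intensity varies between sessions, and no loss if it does not. No bias or power loss is quantified, and the documents do not show which intensity is intended.

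The MEP-size rule is wrong as written, on both the muscle and the starting point of the measurement. It is less serious because the right-FDI trace will exist and can be rescored.

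**What to change.** Reconcile the two silent-period sentences in Single pulse measure. State either one intensity used at every assessment, or that both are conditions and which one is analysed. Name the analysed intensity in TMS Analysis. The choice is for the investigators; nothing in the documents settles it.

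In TMS Analysis, bring the MEP-size rule into line with the listed right FDI, and measure between the peaks of the muscle response, as the paired-pulse trials do.

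This is protocol wording only and adds no procedure. If sessions have already been run, also establish from the records which intensity was used at each, and rescore MEP size from the right-FDI trace. An intensity used at a completed session cannot be changed by rescoring, so the correction is best made early.
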